#### 1.0 Background

Since its clinical introduction in the early 1950s, succinylcholine, a short-acting depolarizing muscle relaxant, has become commonly used for rapid sequence intubation during general anesthesia. In addition to its paralytic effects, succinylcholine administration in general anesthesia carries a multitude of risks, among which are muscle fasciculation and postoperative myalgia. Currently, anesthesiologists are divided in whether rocuronium, a nondepolarizing muscle relaxant, effectively reduces both succinylcholine-induced fasciculations and postoperative myalgias in procedures under general anesthesia. There is sparse and inconsistent literature supporting the efficacy of rocuronium pretreatment for the prevention of succinylcholine-induced fasciculations and postoperative myalgias.

Research into managing the side-effects of using succinylcholine first appeared in 1990 when Pace demonstrated, through a meta-analysis of 45 clinical trials, that nondepolarizing muscle relaxants reduced the frequency of postoperative myalgias by 30%. Rocuronium, while not assessed in Pace's study, is now commonly used to prevent fasciculations and myalgias associated with succinylcholine. Motamed, (1998) demonstrated that pretreatment with rocuronium in elective general surgery reduced the incidence of succinylcholine-induced fasciculations. In laparoscopic procedures in female patients under general anesthesia, Martin et. Al (1998), demonstrated that rocuronium prevented fasciculations but not postoperative myalgias. Likewise, Joshi et. Al (1999) showed that rocuronium prevented succinylcholine-induced fasciculations but failed to prevent myalgias in patients undergoing elective ambulatory surgery with general anesthesia..

In response to the growing literature pertinent to pretreatment of succinylcholine, Schreiber et. al(2005) performed a meta-analysis of 52 randomized trials between 1971 and 2003 to update the aforementioned meta-analysis performed by Pace. Schreiber concluded that doses of 10-30% of the effective dose of nondepolarizing muscle relaxants do significantly decrease the postoperative myalgias and fasciculations. Further, of the nondepolarizing muscle relaxants, rocuronium significantly demonstrated relative risks conferring both effectiveness in reduced fasciculations and 24 hours postoperative myalgia. In 2009, Abbas et. al demonstrated that pretreatment of rocuronium in patients undergoing elective general surgical procedures under general anesthesia decreased the incidence of succinylcholine-induced fasciculations and myalgias; however, in 2014, Kim in elective surgery with general anesthesia, demonstrated that pretreatment with rocuronium reduced fasciculations but did not significantly decrease the incidence of postoperative myalgias.

Previous studies looking at the efficacy of pretreatment with rocuronium to prevent succinvlcholine fasciculations and / or myalgia were limited in many ways including, but not limited to, low numbers in the study groups, a lack of uniformity in the length of the case, and a lack of uniformity in the presence/absence or size of a surgical incision. Studies have demonstrated that patients with little surgical pain are more likely to complain of post-succinylcholine myalgias compared to patients who are preoccupied with terrible pain from surgical wounds. The length of the case also seems to impact the severity of post-surgical muscle pain independent of succinvlcholine use. The actual etiology of postsuccinvlcholine myalgia has not been fully elucidated. It was originally thought that the induction of fasciculations by the acetylcholine-like action of succinvlcholine at the neuromuscular junction caused muscle damage leading to myalgias, however, studies looking at the correlation between fasciculations and myalgias showed only a weak correlation. We hope to address some of these questions with this proposed study. Our group provides anesthesia to patients coming to Indiana University Hospital for ERCP (endoscopic retrograde pancreatography). ERCP cases are generally short (under 2 hours), are uniformly positioned, and do not result in a surgical wound. Because they are such short cases, yet still require general endotracheal anesthesia, succinvlcholine is the drug of choice in our group as it results in rapid intubating conditions with a very short duration of action. As this is a high volume center, we have a unique opportunity to study the effect of pretreatment with a nondepolarizing neuromuscular blocker

(rocuronium) on succinylcholine induced myalgias while enjoying a mitigation of the confounding variables mentioned above.

# Risks:

There is huge variability in the care of patients receiving succinylcholine in the anesthesia community at large and within our own group. Some people believe that succinylcholine should always be pretreated with a non-depolarizing neuromuscular blocker to prevent myalgias, while others believe that it should never be pretreated because, they believe, that the pretreatment doesn't work and is ineffective. This is a proposal to structure that variability into randomized groups and study the outcomes which will lead to a reduction of said variability going forward. There is no added risk to the patient as there is currently no standardization of the practice within our own group. Pretreating and not pretreating are both practiced daily.

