# 3.0 Inclusion/Exclusion Criteria:

Inclusion Criteria:

- Undergoing elective Endoscopic Retrograde Cholangiopancreatography (ERCP) under general anesthesia
- Have been informed of the nature of the study and informed consent has been obtained
- ASA 1, 2 and 3

Exclusion Criteria:

- Patients will be excluded if they have chronic pain requiring daily opioid use greater than 30 mg PO morphine equivalent.
- Patients will also be excluded if their comorbid medical conditions require a true rapid sequence induction as precurarization with rocuronium increases the time to intubation which is undesirable in a patient who is at high risk for aspiration.
- Patients taking muscle relaxants at home for spasticity.
- Patients under the age of 18 years old.
- Any contraindication for using succinylcholine or rocuronium.
- Less than 50kg or greater than 120kg

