# 4.0 Enrollment/Randomization

All Endoscopic Retrograde Cholangiopancreatography (ERCP) procedures scheduled at IU Health University Hospital on adult patients (18+ years old) will be identified. Subjects will be contacted face-toface prior to surgery by one of the research team members. They will be informed about the study and all questions will be answered. The potential subjects will be given a copy of the informed consent form and authorization form. The subjects will then be contacted face-to-face in POCU on the day of surgery and if participation is agreed upon, written consent will be taken. All patients will receive general endotracheal anesthesia consistent with acceptable standards of care.

A total of 300 subjects will be randomized by a/ computer program into 3 groups (100 in each group):

- 1. Group 1 (Control): 0 mg/kg of rocuronium pretreatment and 1 mg/kg (rounded up to the nearest 10 mg) succinylcholine
- Group 2: 0.05 mg/kg (rounded up to the next mg) up to 5 mg of rocuronium pretreatment followed by 1.0 mg/kg (rounded up to the next 10mg) succinlycholine t = 1 min +/- 10 sec after pretreatment.
- 3. Group 3: 0.05 mg/kg (rounded up to the next mg) up to 5 mg of rocuronium pretreatment followed by 1.0 mg/kg (rounded up to the next 10 mg) succinlycholine t = 2 min +/- 10 sec after pretreatment.

Drug amount rounding takes into account the limitations to accurately measure drug doses in the clinical setting. Rocuronium is measured in a 1 ml tuberculin syringe with 1mg = 0.1ml. Rounding allows the provider to round to the next 0.1ml. Smaller increments cannot be accurately measured. Likewise, Succinylcholine is 20mg/ml and administered from a pre-labeled, calibrated 10 ml syringe. The above allowable rounding allows the provider to administer the drug to the next nearest 10mg=0.5ml for the same reason.

Randomization will be performed using Research Randomizer in blocks of 30. The primary investigator will inform the person doing the case as to what group the patients are randomized to. Both the patients and the research staff doing assessments will be blinded to the randomization.

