#### **5.0 Study Procedures**

After IRB approval from Indiana University Hospital and with written and verbal informed consent from each patient, 300 ASA I, II and III outpatients scheduled for elective Endoscopic Retrograde Cholangiopancreatography (ERCP) under general anesthesia will be enrolled in this randomizedcontrolled study. The patients and the study personnel performing post-op assessments will be blinded. Anesthesiologists cannot be blinded during this study since they will be required to draw up the study drugs as well as managing the wait time between rocuronium and succinylcholine. Patients are assigned to one of three groups (n = 100 each group). Each patient will undergo a standard IV induction of anesthesia (Lidocaine 1mg/kg, propofol 1-2 mg/kg titrated to effect, and succinvlcholine (administered as indicated by study group assignment). Study group details are as follows: Group 1 (Control) to receive no rocuronium and 1 mg/kg of succinylcholine (rounded up to the next 10mg). Groups 2 and 3 to receive 0.05 mg/kg (rounded up to the next 1mg) up to 5 mg of rocuronium; patients ranging from 50-120 kg. In Group 2, succinvlcholine administration will occur at 1.0 mg/kg (rounded up to the next 10 mg) at t = 1minute (+/-10 seconds) after pretreatment with rocuronium. In Group 3, succinylcholine 1mg/kg (rounded to the next 10 mg) will be administered at t = 2 minutes (+/- 10 seconds) after pretreatment. The Succinvlcholine-induced fasciculations will be noted on study assessment sheet as either present or absent. Myalgia assessment is to occur succinvlcholine administration at t = 3 hours and t = 24 hours and will be rated as described below.

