#### Myalgia assessment:

Subjects will by queried at the above time points about muscle pain and scored based on their answers as follows.

- 0 no pain / no muscle stiffness
- 1 mild muscle pain and/or stiffness at 1 or more sites that does not limit daily activity
- 2 Moderate muscle pain and/or stiffness at 1 or more sites that does not limit daily activity
- 3 Moderate generalized muscle pain and/or stiffness limiting daily activity

4 – Severe muscle pain and/or stiffness at 1 or more sites limiting movement and preventing daily activity

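### The no-added-risk statement in Section 1.0 does not address the longer time to intubation acknowledged in Section 3.0, and the plan lists no systematic by-arm recording of that cost

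*Combined protocol and SAP*

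**What the plan says.** - **Section 1.0, Risks.** The text states: "There is no added risk to the patient as there is currently no standardization of the practice within our own group". The support offered is that "Pretreating and not pretreating are both practiced daily". The same paragraph expects the findings to narrow that variation in practice.
- **Section 3.0.** One exclusion reads: "Patients will also be excluded if their comorbid medical conditions require a true rapid sequence induction". The reason given is that "precurarization with rocuronium increases the time to intubation which is undesirable in a patient who is at high risk for aspiration".
- **Section 4.0.** Succinylcholine is given at "t = 1 min +/- 10 sec after pretreatment" in Group 2 and at "t = 2 min +/- 10 sec after pretreatment" in Group 3. Group 1 has no pretreatment and so no such interval. The principal investigator tells the person doing the case which group applies.
- **Section 2.0.** The outcomes are myalgia (presence, severity, onset) and its correlation with fasciculation.
- **Section 5.0.** The one outcome listed at induction is fasciculation: "The Succinvlcholine-induced fasciculations will be noted on study assessment sheet as either present or absent". For the 3 h and 24 h contacts the plan says: "Subjects will by queried at the above time points about muscle pain and scored based on their answers as follows". Anaesthesiologists are not blinded.
- **Sections 6.0 and 7.0.** Summaries are given overall and by group. Adverse events that are not endpoints go to the principal investigator. There is no list of events, no active questioning and no by-arm safety table.

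**The concern.** That both practices already occur shows that clinicians here accept the consequences of either. It does not show that the consequences are the same. Randomisation also assigns pretreatment, with a fixed wait, to some patients whose own anaesthesiologist might not have used it. Section 3.0 names one consequence, a longer time to intubation, and the Risks text never mentions it.

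The trial is meant to influence practice. If Group 3 has less myalgia, readers will take that as support for a two-minute wait and will ask what the wait cost. The plan provides no systematic answer. Airway problems would reach the data only if someone who knows the allocation judged them to be adverse events and reported them. A longer but planned time to intubation may well not be judged so.

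**Working it through.** **1. The plan's own figure.** The only design calculation concerns myalgia: 100 per group, 50% reference rate, odds ratio 2.26, two-sided alpha 0.05, 80% power.

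- Second proportion: 2.26 / 3.26 = 0.693. Difference: 0.193. Mean proportion: 0.597.
- z = [0.1933 × √100 − 1.96 × √(2 × 0.597 × 0.403)] / √(0.25 + 0.693 × 0.307) = (1.933 − 1.360) / 0.680 = 0.84, which gives 80.0% power.

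The figure reproduces. It has no bearing on this point.

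**2. The two statements side by side.** Section 1.0 compares taking part with present care in this group. Section 3.0 describes an effect of pretreatment itself, and calls it undesirable for patients at high aspiration risk. Both can be true together, but the first does not answer the second. The exclusion removes the patients for whom the protocol calls the delay undesirable. It does not remove the delay for those who remain.

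**3. Who is exposed.** Groups 2 and 3 make up 200 of 300 patients. The assigned intervals are 60 ± 10 s (50 to 70 s) and 120 ± 10 s (110 to 130 s). These run from rocuronium to succinylcholine. The documents do not say whether rocuronium comes before or after the induction agent, so they do not show how much of the wait falls between induction and intubation.

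**4. What is listed for recording.** Sections 2.0, 5.0, 6.0, 7.0 and 10.0 contain no time to intubation, oxygen saturation, regurgitation, aspiration or other airway outcome. The by-group summaries in Section 6.0 can cover only what is collected.

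**5. What recording could show.**

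*Timing, available from every patient.* The 95% half-width for a difference in means between two arms is 1.96 × SD × √(2/100) = 0.277 SD. The documents give no SD. For assumed values of 30, 60 and 90 s, the half-width is 8.3, 16.6 and 24.9 s.

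*Rare events (rates are assumptions).* The chance of at least one event is 1 − (1 − p)ⁿ:

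| True rate | 100 patients | 200 patients |
|---|---|---|
| 0.1% | 9.5% | 18.1% |
| 0.5% | 39.4% | 63.3% |
| 1% | 63.4% | 86.6% |

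For a comparison of two arms of 100 by Fisher's exact test:

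- 5 events against 0: 2 × (100·99·98·97·96)/(200·199·198·197·196) = 0.059.
- 6 events against 0: the same product extended by 95/195, which gives 0.029.

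Six events against none would be needed to reach 5%. Timing can therefore be compared usefully, while rare airway events can only be described.

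**The case against.** The strongest reply is that the Risks text is about participation against usual care, where both approaches are in daily use, and that Section 3.0 already excludes the patients for whom it calls delay undesirable. For those still eligible, no section calls a longer time to intubation a harm. This stands in part. A reader might infer that the protocol contradicts itself outright, and the documents do not support that. What remains is that the stated reason does not address the acknowledged delay.

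A reader might also infer that the trial can report only the benefit of the waits. That is too strong. The myalgia tests are two-sided and could show no effect or a worse result, and Section 7.0 gives a route by which an airway event could be reported and then tabulated by arm. The gap is the lack of systematic, defined collection.

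It is tempting to argue that spontaneous reports say little because zero events in 100 patients is compatible with a rate up to 1 − 0.025^(1/100) = 3.6%, or 1.8% for zero in 200. Those limits come from the sample size and apply equally to active recording, so they are no argument against spontaneous reports.

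Two further cautions stand. The assessment sheet itself is not shown, so the supported statement is that no airway outcome is listed, not that none will be written down. The consent pages are not available, so nothing can be said about whether patients are told of the delay.

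Finally, recorded timings will partly re-measure a wait that the design fixes. They would still show how far the assigned interval carries through to time to intubation, which the documents leave open.

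**Conclusion.** The point holds in limited form. The no-added-risk statement rests only on variation in current practice and leaves unaddressed the longer time to intubation in Section 3.0, which the exclusion mitigates but does not abolish. The plan lists no systematic by-arm recording of time to intubation or airway events, and it relies on undefined adverse-event reports with unblinded staff at induction. The cost of the assigned waits in two thirds of the patients (200/300) will therefore not be systematically measured.

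Severity is low: no planned myalgia analysis, sample size or error rate is affected. The conclusion rests on reading what the documents list. The timing precision and rare-event figures depend on the assumed SDs and event rates shown, and serve only to indicate what by-arm recording could and could not deliver.

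**What to change.** 1. Reconcile the Risks text in Section 1.0 with Section 3.0, so that the acknowledged effect on time to intubation and the mitigating exclusion appear together. Check that the patient information is consistent with the result.
2. In all three arms, take from the anaesthetic record the times of rocuronium (if given), induction, succinylcholine and intubation, the lowest oxygen saturation before intubation, and any regurgitation or aspiration.
3. In Section 6.0, name these as safety outcomes to be reported descriptively by arm beside myalgia, and state that rare events cannot be compared reliably with 100 patients per arm.
4. Optionally, add one open question about other problems at the existing 3 h and 24 h contacts.

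The cost is a text correction, a few form fields, one descriptive table and slightly more data entry. No dose, waiting interval or sample size changes.

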# 2.0 Rationale and Specific Aims

Our hypothesis is that precurarization with rocuronium, followed by a 2 minute interval prior to administering succinylcholine will prevent, or ameliorate, succinylcholine induced myalgias compared to not pretreating, or pretreating with a shorter time interval prior to succinylcholine administration.

Primary endpoint: Does the patient have myalgias post succinylcholine administration with pretreatment with Rocuronium 2 minutes prior?

Secondary endpoint?

\*Severity of myalgias

\*Onset of myalgias postop relative to succinylcholine administration

\*Correlation of myalgias with the presence of skeletal muscle fasciculation upon succinylcholine administration

# 3.0 Inclusion/Exclusion Criteria:

Inclusion Criteria:

- Undergoing elective Endoscopic Retrograde Cholangiopancreatography (ERCP) under general anesthesia
- Have been informed of the nature of the study and informed consent has been obtained
- ASA 1, 2 and 3

Exclusion Criteria:

- Patients will be excluded if they have chronic pain requiring daily opioid use greater than 30 mg PO morphine equivalent.
- Patients will also be excluded if their comorbid medical conditions require a true rapid sequence induction as precurarization with rocuronium increases the time to intubation which is undesirable in a patient who is at high risk for aspiration.
- Patients taking muscle relaxants at home for spasticity.
- Patients under the age of 18 years old.
- Any contraindication for using succinylcholine or rocuronium.
- Less than 50kg or greater than 120kg

# 4.0 Enrollment/Randomization

All Endoscopic Retrograde Cholangiopancreatography (ERCP) procedures scheduled at IU Health University Hospital on adult patients (18+ years old) will be identified. Subjects will be contacted face-toface prior to surgery by one of the research team members. They will be informed about the study and all questions will be answered. The potential subjects will be given a copy of the informed consent form and authorization form. The subjects will then be contacted face-to-face in POCU on the day of surgery and if participation is agreed upon, written consent will be taken. All patients will receive general endotracheal anesthesia consistent with acceptable standards of care.

A total of 300 subjects will be randomized by a/ computer program into 3 groups (100 in each group):

- 1. Group 1 (Control): 0 mg/kg of rocuronium pretreatment and 1 mg/kg (rounded up to the nearest 10 mg) succinylcholine
- Group 2: 0.05 mg/kg (rounded up to the next mg) up to 5 mg of rocuronium pretreatment followed by 1.0 mg/kg (rounded up to the next 10mg) succinlycholine t = 1 min +/- 10 sec after pretreatment.
- 3. Group 3: 0.05 mg/kg (rounded up to the next mg) up to 5 mg of rocuronium pretreatment followed by 1.0 mg/kg (rounded up to the next 10 mg) succinlycholine t = 2 min +/- 10 sec after pretreatment.

Drug amount rounding takes into account the limitations to accurately measure drug doses in the clinical setting. Rocuronium is measured in a 1 ml tuberculin syringe with 1mg = 0.1ml. Rounding allows the provider to round to the next 0.1ml. Smaller increments cannot be accurately measured. Likewise, Succinylcholine is 20mg/ml and administered from a pre-labeled, calibrated 10 ml syringe. The above allowable rounding allows the provider to administer the drug to the next nearest 10mg=0.5ml for the same reason.

Randomization will be performed using Research Randomizer in blocks of 30. The primary investigator will inform the person doing the case as to what group the patients are randomized to. Both the patients and the research staff doing assessments will be blinded to the randomization.

#### **5.0 Study Procedures**

After IRB approval from Indiana University Hospital and with written and verbal informed consent from each patient, 300 ASA I, II and III outpatients scheduled for elective Endoscopic Retrograde Cholangiopancreatography (ERCP) under general anesthesia will be enrolled in this randomizedcontrolled study. The patients and the study personnel performing post-op assessments will be blinded. Anesthesiologists cannot be blinded during this study since they will be required to draw up the study drugs as well as managing the wait time between rocuronium and succinylcholine. Patients are assigned to one of three groups (n = 100 each group). Each patient will undergo a standard IV induction of anesthesia (Lidocaine 1mg/kg, propofol 1-2 mg/kg titrated to effect, and succinvlcholine (administered as indicated by study group assignment). Study group details are as follows: Group 1 (Control) to receive no rocuronium and 1 mg/kg of succinylcholine (rounded up to the next 10mg). Groups 2 and 3 to receive 0.05 mg/kg (rounded up to the next 1mg) up to 5 mg of rocuronium; patients ranging from 50-120 kg. In Group 2, succinvlcholine administration will occur at 1.0 mg/kg (rounded up to the next 10 mg) at t = 1minute (+/-10 seconds) after pretreatment with rocuronium. In Group 3, succinylcholine 1mg/kg (rounded to the next 10 mg) will be administered at t = 2 minutes (+/- 10 seconds) after pretreatment. The Succinvlcholine-induced fasciculations will be noted on study assessment sheet as either present or absent. Myalgia assessment is to occur succinvlcholine administration at t = 3 hours and t = 24 hours and will be rated as described below.

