#### 6.0 Statistical Analysis

The statistical analysis will be conducted using SAS. Summary statistics will be calculated for the overall cohort, as well as by-treatment group. Categorical variables will be presented as frequencies and percentages, and groups will be compared with chi-square or Fisher's Exact tests. Distributions of the continuous variables will be assessed to determine if data transformations or non-parametric tests are needed. Continuous variables will be presented as mean and standard deviation and groups will be compared with ANOVA unless non-parametric tests are warranted, in which case, median and interquartile range will be calculated and Kruskal-Wallis tests will be used to compare groups. For variables with multiple measurements, these statistics will be given for each discrete time point. Myalgia will be assessed as both a categorical variable (any myalgia vs. none), and as an interval variable. A significance level of 5% will be used for all statistical comparisons.

To determine the effect of the treatments over time on the outcomes of interest, mixed models will be utilized, with fixed effects for treatment and time, as well as their interaction, and a random effect for subject. When necessary, additional variables may be added to adjust the models for other noted differences between the treatment groups.

Based on prior observation, the myalgia incident rate is 50%. With 100 patients in each of the three groups, will have 80% power to detect an odds ratio of 2.26 between any two groups, with two-sided tests and an alpha of 0.05 (5% significance level).

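### Fasciculation is a single unanchored yes/no item with no named recorder, so the fasciculation-myalgia endpoint loses severity and may be hard to interpret if fasciculation is very common or very rare within an arm

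*Combined protocol and SAP*

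**What the plan says.** Protocol Section 5.0 (Study Procedures) states that succinylcholine-induced "fasciculations will be noted on study assessment sheet as either present or absent". The protocol text has no intensity grade, minimum criterion or observation window, and does not say who makes the entry.

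Section 2.0 lists as a secondary endpoint: "Correlation of myalgias with the presence of skeletal muscle fasciculation upon succinylcholine administration". Section 1.0 gives the motive. Fasciculations were once thought to injure muscle and so cause myalgia, but "studies looking at the correlation between fasciculations and myalgias showed only a weak correlation", and the authors hope to address some of these questions.

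On blinding, Section 5.0 says "Anesthesiologists cannot be blinded during this study since they will be required to draw up the study drugs" and "The patients and the study personnel performing post-op assessments will be blinded". Section 4.0 is a little broader: "Both the patients and the research staff doing assessments will be blinded to the randomization". Neither section places a blinded person at induction.

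Section 6.0 says "Myalgia will be assessed as both a categorical variable (any myalgia vs. none), and as an interval variable". It names no coefficient or model for the fasciculation-myalgia association. Its general rule is that categorical variables are compared between groups by chi-square or Fisher's exact test at 5%.

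**The concern.** The two halves of the correlation are measured very unevenly. Myalgia has an anchored 0-4 scale. Fasciculation, the supposed cause, has one tick with no anchor. If the question is whether fasciculation injures muscle, the informative contrast is between faint and vigorous fasciculation, and a yes/no item puts both under 'present'.

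There are two separate consequences.

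1. **Restricted range.** If nearly everyone or nearly no one in an arm fasciculates, a phi-type coefficient has a low ceiling and few patients remain in the smaller category. Another weak correlation could then not be told apart from a limit of the measurement.
2. **Unblinded rating.** Whoever records fasciculation at induction may know the group. With no definition of 'present', borderline cases could be read differently by arm. That would affect the between-group comparison implied by Section 6.0 as well as the association.

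Both bear on a secondary endpoint. The primary myalgia endpoint is not affected.

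**Working it through.** **Inputs from the protocol.** Fasciculation is binary (Section 5.0). There are 100 patients per group, and two of the three groups are pretreated (Section 4.0). For myalgia, Section 6.0 says "Based on prior observation, the myalgia incident rate is 50"%. No fasciculation rate is given anywhere, so every rate below is an assumption.

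**The plan's own figure.** The only calculation stated is 80% power for an odds ratio of 2.26 with 100 per group. From 50% (odds 1), the comparison rate is 2.26/3.26 = 69.3%. A two-sided 5% two-proportion test with 100 per group then has 80.0% power. The figure reproduces and confirms that 50% is the reference myalgia rate, but it says nothing about the correlation endpoint.

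**Ceiling on phi.** For two binary variables, with a the smaller and b the larger rate, phi_max = sqrt[a(1-b) / (b(1-a))]. With myalgia at 50% and fasciculation rate p of at least 50%, this becomes sqrt[(1-p)/p]. At 50% myalgia it is symmetric, so p and 1-p give the same ceiling.

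| Assumed fasciculation rate in the arm | Calculation | Maximum phi |
|---|---|---|
| 50% | sqrt(0.50/0.50) | 1.00 |
| 60% (or 40%) | sqrt(0.40/0.60) | 0.82 |
| 70% (or 30%) | sqrt(0.30/0.70) | 0.65 |
| 80% (or 20%) | sqrt(0.20/0.80) | 0.50 |
| 90% (or 10%) | sqrt(0.10/0.90) | 0.33 |
| 95% (or 5%) | sqrt(0.05/0.95) | 0.23 |

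At 90%, about 10 of 100 patients form the 'absent' category; at 95%, about 5.

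**Lower myalgia.** If an arm has 30% myalgia, the ceilings at 70%, 80% and 90% fasciculation are 0.43, 0.33 and 0.22. The symmetry is then lost: at 10% fasciculation the ceiling is sqrt[(0.10 × 0.70)/(0.30 × 0.90)] = 0.51.

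**Pooling the three arms.** Assume 90% fasciculation in control, a common rate in both pretreated groups, and 50% myalgia overall.

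| Rate in pretreated groups | Pooled rate | Maximum phi |
|---|---|---|
| 30% | (90+30+30)/3 = 50% | 1.00 |
| 50% | (90+50+50)/3 = 63% | 0.76 |
| 70% | (90+70+70)/3 = 77% | 0.55 |
| 90% | 90% | 0.33 |

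Pooling can lift the ceiling, but only by mixing arms whose fasciculation rates differ because of treatment.

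**If an odds ratio is used.** It has no such ceiling, but the small category still costs precision. For illustration, take the plan's odds ratio of 2.26 as the fasciculation-myalgia association within one arm of 100, with 50% myalgia overall. A two-sided 5% two-proportion test has about 52% power if half fasciculate, 20% at 90% and 12% at 95%.

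**The case against.** The strongest reply is that the record does what the endpoint asks: Section 2.0 speaks of the presence of fasciculation, and Section 5.0 records presence. That stands. This is a weakness of design, not a contradiction, and the Background commits only to addressing some of the open questions.

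A reader might go further and infer that the correlation must be weak whenever most patients fasciculate. The documents do not support that. At 50% myalgia the ceiling is still 0.82 at 60% fasciculation and 0.50 at 80%; it nears 0.3 only at about 90% or more, and no rate is given. The ceiling belongs to phi-type coefficients, and Section 6.0 names none. Nor does lack of blinding create it; that is a separate problem.

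Pooling is a fair point too, since two of the three groups are pretreated. But Section 1.0 cites studies in which rocuronium reduced fasciculation, and Section 2.0 hypothesizes that it reduces myalgia. A pooled correlation would therefore partly reflect treatment, and the plan does not say whether the analysis is within arm, adjusted or pooled.

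A reader might also infer that unblinded raters would tick 'absent' too often in pretreated patients and produce a false group difference. That is not shown. The Risks text in Section 1.0 describes opposing beliefs about pretreatment, chiefly about myalgia, so no net direction follows. Nor can a size be given. Misreading in one arm only, between arms with equal true rates, fits neither control against pretreated (reductions are cited) nor Group 2 against Group 3 (both pretreated).

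Finally, the study assessment sheet is not among the documents. The absence of a definition or window is shown for the protocol text only.

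**Conclusion.** The point holds in a limited form, as a cheap improvement to a secondary endpoint. The protocol gives a binary item without anchors, names no recorder and places no blinded observer at induction. The loss of severity information is certain and cannot be repaired after the event.

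The restriction on the correlation is conditional. It matters if fasciculation within an arm is roughly 90% or more, or 10% or less, at 50% myalgia (ceiling 0.33 or lower). It is moderate at 80% or 20% (0.50) and mild nearer the middle. 'Weak' is taken here as about 0.3; the documents set no threshold. Arm-dependent reading by an unblinded recorder is possible, but its direction and size are unknown.

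**What to change.** - **Section 5.0:** replace the present/absent entry with an anchored ordinal grade, scored over a fixed window after succinylcholine by the person already observing. For example: 0 none; 1 fine, confined to face, neck or fingertips; 2 moderate, more than one region or visible limb twitch; 3 vigorous or generalized with limb movement. Keep 'any (grade 1 or more)' as the binary summary, so that the current endpoint is preserved.
- **Section 5.0:** state who records fasciculation and whether that person knows the group. If unblinded, report the between-group comparison of fasciculation as descriptive.
- **Section 2.0, with a matching line in Section 6.0:** define the endpoint as the association of fasciculation grade with myalgia grade, analysed within or adjusted for randomized group, and name the measure.

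The cost is one line on the form and a few wording changes, with no extra staff or procedure. The downsides are slightly more recording at induction and a rating that stays unblinded if the anesthesiologist makes it. Anchors narrow the room for judgement but do not remove it.
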